3.5 Lymphocytosis

MCL:

Upon initiation of ibrutinib a temporary increase in lymphocyte counts (ie $\geq 50\%$ increase from baseline and above absolute lymphocyte count of 5,000/mcL) occurred in 33% of patients in the MCL study. The onset of isolated lymphocytosis occurs during the first few weeks of ibrutinib therapy and resolves by a median of 8 weeks.

Patients with MCL who develop lymphocytosis greater than 400,000/mcL have developed intracranial hemorrhage, lethargy, gait instability, and headache. However, some of these cases were in the setting of disease progression.

CLL:

Upon initiation of ibrutinib a temporary increase in lymphocyte counts (ie $\geq 50\%$ increase from baseline and above absolute lymphocyte count of 5,000/mcL) in 77% of patients in the CLL study. The onset of isolated lymphocytosis occurs during the first month of ibrutinib therapy and resolves by a median of 23 weeks (range 1 - 104+ weeks).

3.6 Supplier

Ibrutinib used under this study will be provided by Janssen Scientific Affairs and will be identical to the commercially marketed product.

3.7 Drug Accountability

The sponsor-investigator, or a responsible party designated by the sponsor-investigator, must maintain a careful record of the receipt, disposition, and return of all drugs received for this study using the study specific Investigational Agent Accountability Record form or NCI Drug Accountability form.

Return of unused ibrutinib

Patients will be instructed to return unused ibrutinib to the SCCA pharmacy. All unused drug will be destroyed per Investigational Drug Services policy.

4.0 STAGING CRITERIA

- 4.1 When applicable, the Ann Arbor staging criteria (see Appendix A) will be used; staging should be the highest stage established, either at diagnosis or relapse of disease.
- 4.2 For patients from whom data are available, the international prognostic score at the time of diagnosis and enrollment will be documented as detailed below:
 1. Age > 60 years
 2. Ann Arbor stage III or IV
 3. Elevated serum LDH
 4. ECOG PS (see Appendix B) > 1
 5. More than 1 extra-nodal site of disease

5.0 ELIGIBILITY CRITERIA

5.1 Inclusion Criteria

- 5.1.1 Patients must have histologically confirmed transformed indolent B-cell non-Hodgkin lymphoma that is relapsed or refractory to at least one line of therapy.
- 5.1.2 Patients must have a CT (preferred) or MRI scan of the chest, abdomen, and pelvis within 28 days of enrollment.
- 5.1.3 Patients must have measurable disease defined as lesions greater than 1.5 cm that can be accurately measured in two dimensions by CT (preferred), or MRI.
- 5.1.4 Patients must have a PET scan within 56 days of enrollment.
- 5.1.5 Patients must have an ECOG performance status of 0 to 2 (See Appendix B).
- 5.1.6 Patients must be 18 years of age or older.

5.1.7 Hematology values must be within the following limits independent of growth factor or transfusion support:

5.1.7.1 Absolute neutrophil count (ANC) $\geq 1000/\text{mm}^3$ or $\geq 750/\text{mm}^3$ in the setting of marrow involvement by disease.

5.1.7.2 Platelets $\geq 50,000/\text{mm}^3$ or $\geq 30,000/\text{mm}^3$ in the setting of marrow involvement by disease or splenomegaly due to disease.

5.1.8 Biochemical values within the following limits:

5.1.8.1 Alanine aminotransferase (ALT) and aspartate aminotransferase (AST) $\leq 3 \times$ upper limit of normal (ULN)

5.1.8.2 Total bilirubin $\leq 1.5 \times$ ULN unless bilirubin rise is due to Gilbert's syndrome or of non-hepatic origin

5.1.8.3 Creatinine clearance (Clcr) $> 25 \text{ mL/min}$

5.1.9 Patients must be anticipated to complete 2 cycles of therapy in the opinion of the treating physician.

5.1.10 Women of childbearing potential and men who are sexually active must affirm they are practicing a highly effective method of birth control during and after the study consistent with local regulations regarding the use of birth control methods for subjects participating in clinical trials. Men must agree to not donate sperm during or after the study. For females, these restrictions apply for 1 month after the last dose of study drug. For males, these restrictions apply for 3 months after the last dose of the study drug.

5.1.11 Women of childbearing potential must have a negative serum (beta-human chorionic gonadotropin [β -hCG]) or urine pregnancy test at Screening. Women who are pregnant or breastfeeding are ineligible for this study.

5.1.12 Sign (or their legally-acceptable representatives must sign) an informed consent document in accordance with institutional and federal guidelines indicating that they understand the investigational nature of and procedures required for the study, including biomarkers, and are willing to participate in and comply with the guidelines of the study.

5.2 Exclusion Criteria

5.2.1 Known history of human immunodeficiency virus (HIV) or active Hepatitis C Virus or active Hepatitis B Virus infection or any uncontrolled active systemic infection.

5.2.2 Major surgery or a wound that has not fully healed within 4 weeks of initiation of therapy.

5.2.3 Known central nervous system lymphoma.

- 5.2.4 History of stroke or intracranial hemorrhage within 6 months of screening.
- 5.2.5 Requires anticoagulation with warfarin or equivalent vitamin K antagonists (e.g., phenprocoumon).
- 5.2.6 Requires chronic treatment with strong CYP3A inhibitors.
- 5.2.7 Clinically significant cardiovascular disease such as uncontrolled or symptomatic arrhythmias, congestive heart failure, or myocardial infarction within 6 months of screening, or any Class 3 (moderate) or Class 4 (severe) cardiac disease as defined by the New York Heart Association Functional Classification.
- 5.2.8 Vaccinated with live, attenuated vaccines within 4 weeks of initiation of therapy.
- 5.2.9 Any life-threatening illness, medical condition, or organ system dysfunction which, in the investigator's opinion, could compromise the subject's safety, interfere with the absorption or metabolism of ibrutinib capsules, or put the study outcomes at undue risk.
- 5.2.10 Patients with other prior malignancies except for adequately treated basal cell carcinoma, squamous cell carcinoma of the skin, breast or cervical cancer *in situ*, or other cancer from which the patient has been disease-free for 5 years or greater, unless approved by the protocol Sponsor-Investigator / Lead-Sub-Investigator.
- 5.2.11 Patients that previously were treated with ibrutinib for > 7 days.
- 5.2.12 Previous chemotherapy, immunotherapy, biologically targeted therapy, other investigational agent, or radiation therapy within 3 weeks of initiation of ibrutinib therapy or radio-immunotherapy within 12 weeks of initiation of ibrutinib therapy.
- 5.2.13 Prior allogeneic transplant with GVHD requiring immunosuppressive therapy.

- 5.3 Restrictions: The following guidance should be considered during the perioperative period for subjects who require surgical intervention (including oral surgery) or an invasive procedure while receiving ibrutinib:
 - 5.3.1 For any planned surgery or invasive procedure requiring sutures or staples for closure, ibrutinib should be held at least 7 days prior to the intervention and should be held at least 7 days after the procedure, and restarted at the discretion of the investigator when the surgical site is reasonably healed without serosanguineous drainage or the need for drainage tubes.
 - 5.3.2 For planned minor procedures (such as a central line placement, needle biopsy, thoracentesis, or paracentesis) ibrutinib should be held for at least 3 days prior to the procedure and should not be restarted for at least 3 days after the procedure. For bone marrow biopsies that are performed while the subject is on ibrutinib, it is not necessary to hold ibrutinib for these procedures.

5.3.3 For emergency procedures, ibrutinib should be held after the procedure until the surgical site is reasonably healed, for at least 7 days after the urgent surgical procedure or at the discretion of the investigator.

6.0 REGISTRATION

6.1 Patients must be registered prior to the start of protocol therapy. A completed eligibility checklist with source documentation, a copy of the signed consent form and a signed HIPAA authorization are required for registration. All of the eligibility requirements according to Section 5.0 must have been met.

7.0 TREATMENT PLAN

7.1 For treatment or dose-modification related questions, please contact [name] at [contact] or [name] at [contact]. (MedCon may also be used to contact MDs at [contact].)

7.2 Administration of ibrutinib. Ibrutinib is taken orally at a dose of 560 mg daily.

Drug	Dose	Route	Days	Duration
Ibrutinib	560 mg	PO	Once daily	Until disease progression, intolerance, or decision of patient or treating physician

Post Protocol Follow-up

Long-term follow-up will assess survival and disease progression; subjects will be contacted until death, subject withdrawal of consent, lost to follow-up, or study termination by the sponsor-investigator, whichever occurs first.

7.3 Prophylaxis

No prophylaxis is needed for ibrutinib and supportive care should be administered as needed.

7.4 Criteria for removal from protocol treatment:

7.4.1 Documented progression of disease (see section 10.6).

7.4.2 Development of any related non-hematologic grade ≥ 4 toxicity or other serious adverse event as defined in section 12.0 will qualify for consideration from removal from protocol treatment

7.4.3 Development of any other unacceptable toxicity

7.4.4 Delay of treatment for more than 21 days due to adverse events.

7.4.5 The patient may withdraw from the treatment at any time for any reason.

7.4.5 Taking prohibited medications concurrent with ibrutinib therapy may result in removal from protocol treatment.

7.5 Continuation of therapy after disease progression
 Anecdotal reports indicate that cessation of ibrutinib in patients with B-NHL may contribute to rapid tumor progression. Consequently, it may be beneficial for patients to begin a new treatment regimen after a minimal interval off ibrutinib. To facilitate this, ibrutinib may be continued for up to 4 weeks after documentation of disease progression provided that all other criteria for continuation of treatment are met. Ibrutinib must be stopped at least 24 hours prior to the initiation of the new B-NHL treatment regimen.

8.0 DOSAGE MODIFICATIONS

8.1 Dose Modification and Dose Delay

Treatment with ibrutinib should be held for any of the toxicities listed below:

- 8.1.1 Grade 4 neutropenia (ANC < 500/mm³)
- 8.1.2 Grade 3 thrombocytopenia (platelets < 50,000/mm³) in the presence of significant bleeding (\geq Grade 2 bleeding)
- 8.1.3 Grade 4 thrombocytopenia (platelets < 25,000/mm³)
- 8.1.4 Grade 3 or Grade 4 nausea, vomiting or diarrhea (if persistent despite optimal antiemetic or antidiarrheal therapy) or any other Grade 4 or unmanageable Grade 3 drug-related toxicities.

The following actions should be taken for drug-related toxicities:

Occurrence of the Same Adverse Event	Action
First	Hold ibrutinib until recovery to Grade ≤ 1 or baseline; may restart at original dose level
Second	Hold ibrutinib until recovery to Grade ≤ 1 or baseline; restart at 1 dose level lower (420 mg daily)
Third	Hold ibrutinib until recovery to Grade ≤ 1 or baseline; restart at 1 dose level lower (280 mg daily)
Fourth	Discontinue ibrutinib

Ibrutinib may be held for a maximum of 21 consecutive days. Ibrutinib should be discontinued if the treatment cannot be resumed within 21 days. Once the ibrutinib dose is reduced because of toxicity, it cannot be re-escalated. No dose escalation of ibrutinib (above 560 mg) is allowed in this study. Refer to section 3.4 for subjects requiring the initiation of anticoagulants while receiving study

drug and for instructions on dose modification or temporary hold during concomitant administration of CYP3A inhibitors or inducers. Refer to section 5.3 for guidance on dose delays during the perioperative period for subjects who require surgical intervention or an invasive procedure while receiving study drug.

If there is a rapid increase in disease burden leading to an "apparent" response of PD after the study drug has been held for at least 7 consecutive days, an assessment response of tumor flare may be assigned instead of PD. Should this occur the patient may remain on study drug if they otherwise meet criteria to continue until the next restaging exam unless there is ongoing evidence of progressive disease before that time despite ongoing treatment. If there is further documented PD on or before the next restaging evaluation the patient will be considered to have PD and the date of PD will be assigned to the initial date tumor flare.

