8.2 Dose Modifications for Adverse Reactions

For adverse reactions listed in Table 1, interrupt IMBRUVICA therapy. Once the adverse reaction has improved to Grade 1 or baseline (recovery), follow the recommended dosage modifications.

Table 1. Recommended Dosage Modifications for Adverse Reactions

Adverse Reaction ^{a,b}	Occurrence	Dose Modification for MCL and MZL After Recovery Starting Dose = 560 mg	Dose Modification for CLL/SLL, WM, and cGVHD After Recovery Starting Dose = 420 mg
Grade 2 cardiac failure	First	Restart at 420 mg daily ^c	Restart at 280 mg daily ^c
	Second	Restart at 280 mg daily ^c	Restart at 140 mg daily ^c
	Third	Discontinue IMBRUVICA	Discontinue IMBRUVICA
Grade 3 cardiac arrhythmias	First	Restart at 420 mg daily ^c	Restart at 280 mg daily ^c
	Second	Discontinue IMBRUVICA	Discontinue IMBRUVICA
Grade 3 or 4 cardiac failure Grade 4 cardiac arrhythmias	First	Discontinue IMBRUVICA	Discontinue IMBRUVICA
Other Grade 3 or 4 non-hematological toxicities ^d Grade 3 or 4 neutropenia with infection or fever Grade 4 hematological toxicities	First	Restart at 420 mg daily	Restart at 280 mg daily
	Second	Restart at 280 mg daily	Restart at 140 mg daily
	Third	Discontinue IMBRUVICA	Discontinue IMBRUVICA

^a See *Warnings and Precautions*.

^b Grading based on National Cancer Institute-Common Terminology Criteria for Adverse Events (NCI-CTCAE) criteria, or International Workshop on Chronic Lymphocytic Leukemia (iwCLL) criteria for hematologic toxicities in CLL/SLL.

^c Evaluate the benefit-risk before resuming treatment.

^a For Grade 4 non-hematologic toxicities, evaluate the benefit-risk before resuming treatment. These updated dosage modification recommendations may reduce the occurrence of additional serious events and are intended to improve tolerability for continued Imbruvica treatment.

Summary of updated dosage modification recommendations:

- Resume ibrutinib treatment at a reduced dose for patients who experience specific non-hematologic and hematologic adverse drug reactions, including Grade 2 cardiac failure and Grade 3 cardiac arrhythmias, as outlined in *Table 1*
- Evaluate the benefit-risk before resuming ibrutinib treatment following Grade 2 cardiac failure, Grade 3 cardiac arrhythmias, or other Grade 4 non-hematological adverse reactions
- Discontinue treatment for patients who experience adverse drug reactions of Grade 3 or 4 cardiac failure or Grade 4 cardiac arrhythmia

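### Section 8.1 gives two dose instructions per row, and they disagree once each of two different toxicities has recurred

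*Combined protocol and SAP*

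**What the plan says.** Section 7.2 sets the starting dose: "Ibrutinib is taken orally at a dose of 560 mg daily". The action table in section 8.1 is headed "Occurrence of the Same Adverse Event", so each toxicity carries its own count. Its four rows work as follows:

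- At a first episode, once recovered, the patient "may restart at original dose level". No mg figure is printed.
- At a second episode the instruction is "Hold ibrutinib until recovery to Grade ≤ 1 or baseline; restart at 1 dose level lower (420 mg daily").
- At a third episode the row repeats that instruction, again with both a relative step and a bracketed figure, now 280 mg.
- At a fourth episode treatment ends.

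The text below the table adds: "Once the ibrutinib dose is reduced because of toxicity, it cannot be re-escalated".

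Section 8.1 does not say how counts for different events combine, whether the bracketed dose or the relative step governs, or what one level below 280 mg would be. Section 8.2 holds a second table with fixed doses only, introduced by "Once the adverse reaction has improved to Grade 1 or baseline (recovery), follow the recommended dosage modifications". It does not say that it replaces 8.1.

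**The concern.** Rows two and three each tell the clinician two things: go down one level, and give a stated dose. These are the same instruction only if the patient is at the level the row assumes, namely 560 mg before row two and 420 mg before row three. Counting per event removes that guarantee, because another toxicity may already have lowered the dose.

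A related conflict sits in row one. If a patient already reduced for one toxicity has a first episode of another, the row allows a return to the original level. If that means 560 mg, it contradicts the ban on re-escalation.

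What is at stake is that two treating clinicians, each able to point to the text, could choose different doses for the same patient after the same history. That is a contradiction in a stated safety rule. It also makes dosing inconsistent for the affected patients, whose experience feeds the tolerability objective (1.2.1).

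**Working it through.** **Inputs.** Starting dose 560 mg (7.2). Levels named in 8.1: 420 and 280 mg below the start. Counts run per event (8.1 table header). A dose reduced for toxicity is not raised (8.1, below the table).

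**Two readings of rows two and three.**
- Fixed: second occurrence = 420 mg, third = 280 mg.
- Relative: new dose = the level next below the current one, in the list 560, 420, 280.

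**One recurring toxicity (the plan's own ladder).** Fixed: 560, 420, 280, discontinue. Relative: 560, 420, 280, discontinue. The two agree at every step, so the table is sound for the case it seems to have been written for.

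**Two toxicities, worked examples.** First occurrences are taken as a return to the dose held, and re-escalation is never allowed. Both choices favour the plan.

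| Order | Dose when B occurs a second time | Printed dose | One level lower |
|---|---|---|---|
| A, B, A, B | 420 mg | 420 mg (no change) | 280 mg |
| A, A, A, B, B | 280 mg | 420 mg (barred increase) | none listed |

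In the first example the readings differ by 420 − 280 = 140 mg, or 140/420 = 33% of the printed dose. In the second, neither half of the row can be followed. The discontinuation row does not apply either, because B has occurred only twice.

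**All orderings, same favourable assumptions.**
- Two episodes of each toxicity: 4!/(2!·2!) = 6 orderings. The printed dose and the relative step disagree at some step in 6 of 6. The printed dose exceeds the current dose in 0 of 6.
- Three episodes of each: 6!/(3!·3!) = 20 orderings. They disagree in 20 of 20. The printed dose exceeds the current dose in 8 of 20, and the re-escalation sentence bars every one of these. The relative reading runs past 280 mg in 20 of 20.

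**Sensitivity to row one.** If the original level is read as 560 mg, orderings in which some row points upward rise from 0 to 2 of 6 and from 8 to 12 of 20. These too are barred.

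**Where the fixed and relative instructions do not conflict.** Let A occur once and B three times (4 orderings). With A's single episode restarting at the dose held, the readings agree in 4 of 4. So this conflict needs at least two episodes of each toxicity. The row-one conflict needs less: a reduction for one toxicity, then a first episode of another.

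**The case against.** **The ban on re-escalation settles it.** In part. Read as a whole, 8.1 never permits a higher dose after a toxicity reduction, and row one only says that the patient may restart. A reader might infer that the protocol instructs a dose increase. It does not. But the sentence names no dose to give instead, and in A, B, A, B there is no increase to block: 420 versus 280 mg stays open.

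**Section 8.2 governs, and is the larger matter.** Section 8.2 calls its recommendations updated, and it covers many of the same events. Under its table a third occurrence of most listed events ends treatment, so a patient at 280 mg after a third episode would not arise for those events. That is a good reason to reconcile both tables together. But 8.2 does not state that it replaces 8.1, its columns name other diseases, and it does not list Grade 3 thrombocytopenia with bleeding, which is a hold trigger in 8.1.2.

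**It will be rare, and there are other routes.** This stands as to size. The enumeration is conditional on several hold-level episodes and weights orderings equally; it says nothing about how often they happen. Section 11.1 describes short survival, section 7.1 names contacts for dose-modification questions, and section 7.4.3 and the physician's discretion in 7.2 allow treatment to stop. These routes limit the harm, but they do not make the rows agree.

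**The tolerability results would be uninterpretable.** A reader might infer this, but the documents do not support it. Objective 1.2.1 names no dose-intensity or discontinuation measure, section 12.14 requires protocol therapy to be documented, and section 11.1 makes secondary analyses mainly descriptive. Nor do the documents support divergence between sites as the mechanism: the trial is run by one cancer center with its university partner.

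**Conclusion.** The point holds in a limited form. The second- and third-occurrence rows of 8.1 contradict themselves once two different toxicities have each caused at least two holds. This is so in every ordering tested (6 of 6 and 20 of 20), even on the assumptions kindest to the plan. Separately, row one conflicts with the re-escalation sentence for an already reduced patient, but only if the original level means 560 mg.

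The result rests on counting per event, as the table header says, and on 8.1 remaining in force beside 8.2. The counts of orderings show that the conflict is structural; they are not a prevalence.

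The reach is limited to patients with more than one toxicity among an estimated 20, where one such patient is 1/20 = 5% of the study. The effect is on consistency of dosing and on the descriptive tolerability objective. Overall response rate, the sample size and error rates are not affected. The table should be corrected, but the point does not put the trial's main conclusion in doubt.

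**What to change.** The sponsor-investigator should reconcile the rows of the 8.1 table with each other, with the re-escalation sentence and with section 8.2. The revised text should:

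- define each step once, so that no row carries two instructions that can differ;
- say what the original dose level means for a patient whose dose has already been reduced;
- say whether occurrences are counted per event or across events;
- say what follows when the lowest listed level has been reached;
- say which of 8.1 and 8.2 applies to events that both cover.

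Which dose or rule applies is a clinical decision for the sponsor-investigator, and none is proposed here. The cost is rewording one table and adding a cross-reference in the next amendment, with no added patients, visits or procedures. A quick test of the new wording is to run A, B, A, B and A, A, A, B, B through it and check that each step gives exactly one permitted action.

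### Sections 8.1 and 8.2 set different doses after repeat severe toxicity (420 mg versus 280 mg at the second event, 280 mg versus stopping at the third), and nothing says which governs

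*Combined protocol and SAP*

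**What the plan says.** Section 7.2 starts every patient on 560 mg daily.

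Section 8.1 lists toxicities for which ibrutinib is held: Grade 4 neutropenia, Grade 4 thrombocytopenia, Grade 3 thrombocytopenia with significant bleeding, persistent severe gastrointestinal toxicity, "or any other Grade 4 or unmanageable Grade 3 drug-related toxicities". A table follows, introduced by "The following actions should be taken for drug-related toxicities". After a first occurrence the patient "may restart at original dose level". After a second the entry is "Hold ibrutinib until recovery to Grade ≤ 1 or baseline; restart at 1 dose level lower (420 mg daily", and after a third "Hold ibrutinib until recovery to Grade ≤ 1 or baseline; restart at 1 dose level lower (280 mg daily". Ibrutinib is discontinued at the fourth.

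Section 8.2 then gives Table 1. Its last row covers Grade 3 or 4 non-hematological toxicity outside the cardiac rows, together with "Grade 3 or 4 neutropenia with infection or fever Grade 4 hematological toxicities". In the column for a 560 mg starting dose, that row gives 420 mg after the first occurrence, 280 mg after the second, and discontinuation at the third. On cardiac events the summary under Table 1 says "Discontinue treatment for patients who experience adverse drug reactions of Grade 3 or 4 cardiac failure or Grade 4 cardiac arrhythmia". Of its own status, 8.2 says: "These updated dosage modification recommendations may reduce the occurrence of additional serious events".

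Section 8.1 refers the reader to Sections 3.4 and 5.3 but never to 8.2, and 8.2 does not mention 8.1.

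**The concern.** Both sections are current text and both instruct the clinician what to do after the same toxicities. At the second and third occurrence they prescribe different actions. Following 8.1 would re-expose a patient after repeated serious toxicity at a higher dose than Table 1 allows, or past the point where Table 1 ends treatment. Treatment continues until progression, intolerance or a decision to stop, so repeat events are foreseeable.

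There is a secondary cost to interpretation. Tolerability is a secondary objective (1.2.1). If some clinicians use 8.1 and others 8.2, the dose reductions and discontinuations reported will partly reflect which section was read. Capture of adverse events is not affected, nor is the definition of the response endpoint.

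**Working it through.** The plan states no figure to reproduce. The check sets the two tables side by side for events that both cover.

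**Inputs.** Starting dose 560 mg (7.2); sequence and triggers from 8.1; last row of Table 1, 560 mg column (8.2); cycle length 21 days (Schema).

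**Overlap.** Grade 4 neutropenia and Grade 4 thrombocytopenia are named in 8.1 and fall under Grade 4 hematological toxicity in Table 1. Drug-related Grade 4 or unmanageable Grade 3 toxicity that is neither cardiac nor hematological is caught by 8.1.4 and by the last row of Table 1.

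| Occurrence | 8.1 | Table 1, 560 mg column | Relation |
|---|---|---|---|
| First | up to 560 mg (permitted) | 420 mg | 8.1 looser, but optional |
| Second | 420 mg | 280 mg | conflict |
| Third | 280 mg | discontinue | conflict |
| Fourth | discontinue | already off drug | none |

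**Size.**

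- Second occurrence: 420 − 280 = 140 mg/day, and 140/280 = 50% above the Table 1 dose. Per cycle: 420 × 21 = 8,820 mg against 280 × 21 = 5,880 mg, a difference of 2,940 mg.
- Third occurrence: 280 × 21 = 5,880 mg per cycle against none.
- Restarts before stopping: three under 8.1 (up to 560, then 420, 280 mg) and two under Table 1 (420, 280 mg).
- First occurrence: 560 − 420 = 140 mg/day, and 140/420 = 33% above Table 1. Because 8.1 only permits this dose, a clinician who restarts at 420 mg complies with both sections.

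**Cardiac events.** The 8.1.4 trigger has no cardiac exception. It therefore permits a restart at up to 560 mg after a first Grade 4 cardiac failure or arrhythmia, where Table 1 discontinues. This too is a permission, and stopping satisfies both sections. A second unmanageable Grade 3 arrhythmia is a further direct conflict: 8.1 gives 420 mg and Table 1 discontinues.

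**Which column.** Table 1's columns name diseases other than transformed lymphoma, but the starting-dose header points to the 560 mg column for every patient. If the 420 mg column were used for, say, transformed CLL, the second-occurrence dose would be 140 mg and the gap would widen to 420 − 140 = 280 mg/day.

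**Search for a precedence rule.** Three provisions come close. Section 8.2 calls its recommendations updated. Section 7.4.2 makes related non-hematologic toxicity of Grade 4 or higher, or another serious adverse event, a ground for considering removal. Section 7.1 gives a contact for dose-modification questions. None says which section governs. Section 7.4.2 sets no dose and does not reach a Grade 4 cytopenia that is not serious.

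**The case against.** The strongest case against has four parts.

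1. *Stopping is always allowed.* Section 7.2 lets the treating physician end treatment and 7.4.3 lists unacceptable toxicity as a removal criterion, so a clinician who stops at the third event breaches nothing. That is true, but a general discretion to stop does not reconcile two directive sequences. Section 8.1 still tells its reader to restart at 280 mg.

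2. *The 420 mg step assumes a restart at 560 mg.* For a patient already at 420 mg under Table 1, one level lower would be 280 mg, which agrees with Table 1. This shows that 8.1 is ambiguous for that patient. The printed figure is nevertheless 420 mg, which would then be no reduction at all.

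3. *Section 8.2 is plainly the newer rule.* Its wording says so, and its cardiac stop instruction is specific where 8.1.4 is generic. That is probably the intent. But it has to be inferred, and a clinician who reads the complete sequence in 8.1 has no reason to look further or to use the 7.1 contact.

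4. *The scale is small.* Total enrollment is estimated at 20 (11.3), the direct conflict needs at least a second qualifying event with each hold resolved within 21 days, and therapy given is documented (12.14), so actual doses remain visible. This stands as a limit on how many patients are affected and on the harm to analysis. It does not excuse contradictory instructions on re-exposure after severe toxicity.

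It is also fair that the documents do not show a 560 mg restart after a first event to be harmful. They say only that the updated rules may reduce further serious events.

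**Conclusion.** The concern holds and should be corrected. For Grade 4 hematological toxicity, and for Grade 4 or unmanageable Grade 3 toxicity that is neither cardiac nor hematological, the two sections cannot both be followed as written at the second occurrence (a 50% difference in daily dose) or the third (280 mg daily against stopping). The first-occurrence dose and the restart after a Grade 4 cardiac event are looser permissions in 8.1, not contradictions.

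This rests on three assumptions: the 560 mg column applies; the same drug-related event recurs, so that both sections count occurrences alike; and each hold resolves within the 21 days allowed. The documents do not say how often repeat events occur or how many patients remain on drug, so the number affected cannot be estimated.

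**What to change.** State in 8.1 that Table 1 of 8.2 prevails for every event it lists, using the 560 mg starting-dose column for all patients whatever the underlying histology. Limit the 8.1 sequence to events outside Table 1, such as Grade 3 thrombocytopenia with Grade 2 bleeding (8.1.2). Where that bleeding is itself Grade 3 or 4, it is a Table 1 event and the precedence sentence covers it. Merging the two into one table would serve equally well.

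One consequence should be made explicit. Table 1 interrupts and reduces for all other Grade 3 non-hematological toxicity, whereas the general trigger in 8.1.4 requires Grade 3 toxicity to be unmanageable. Giving Table 1 precedence settles this in favour of the stricter rule, which 8.2 already requires.

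The cost is amendment wording and site notification, with no added procedures or patients.
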